3.6 Materials

For the duration of the study, the patient will be provided with:

- **Weekly patches:** these weekly patches go directly on the knee. Initially the patient will be provided with 9 x 2 weekly patches, upon request more weekly patches can be obtained through the surgeon clinic.
- **Daily patches:** the daily patches are used to connect the sensors to the weekly patches and shall be replaced every time the sensors come off the leg. Initially the patient will be provided with 63 x 2 daily patches though refill packs can be provided through the surgeon clinic should the patient run out of patches.
- **Box:** including two sensor nodes, a charger with power cord, instructions for use and a sensor alignment block

The accompanying MotionSense mobile application will be available for download through the app store. The patient will be assisted with this installation process by the research nurse involved in onboarding the patient.

3.7 Participants

The study participant will represent a range of typical intended users of the Motionsense System. More specifically, the following selection criteria will be used:

- Planned to undergo unilateral total knee surgery in the coming 4 weeks
- Age 50 to 80
- BMI not exceeding 35
- Owns a smartphone (agnostic to brand or type)
- Patient does not have severe skin conditions that would potentially result in irritation or harming the skin when applying the weekly patches.

Beyond that, the study should aim to recruit patients with various socio-economic backgrounds, various levels of motivation as well as a wide range of educational level.

A total of 50 participants will be recruited for the study. Recruitment for this study will be managed by the Principal Investigator. Through the orthopaedic practice, the surgeon office has regular access to patients matching the profile of intended users. In addition, the surgeon has close contact with the participating physiotherapists while the research nurse is employed by the surgeon office. Participants will provide their written informed consent prior to participation (Appendix F).

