1.0 Introduction

To date a number of studies have been performed to inform the design of the Motionsense wearable hardware and mobile application (Figure 1). This wearable system will seek FDA Class I status (see Appendix F1-4) and allows evaluating the knee flexion angle during activities of daily living and during physiotherapy, while also tracking secondary metrics (often derived from the knee flexion). This system consists of two sensor nodes that are placed above and below the knee joint respectively. This is achieved by means of daily and weekly patch, whereby the weekly patches are first applied to the patients' skin and intended to stay on for at least a week. Subsequently, the daily patches connect the sensor nodes to these weekly patches. The sensor nodes shall thus be removed daily as they require daily (overnight) charging. A detailed description of the system is provided in Appendix A.

[figure not shown]

Figure 1 – Schematic design of the Motionsense system consisting of sensor nodes (left), daily and weekly patches (middle) and mobile application (right).

The data collected through the wearable and mobile app are shared with a cloud infrastructure, hereafter referred to as OrthoLogIQ. This is a HIPAA compliant database infrastructure that provides the surgeon and care team with remote access to the patient profile to review the daily activity data, assigned home exercise program and compliance therewith, pictures uploaded by the patient, ...

A primary outcome from these wearable devices is the knee range of motion, absolute knee flexion angle, knee active time, steps and successful repetitions of prescribed physiotherapy exercises. These metrics are tracked and reported by the companying mobile application.

During the proposed study, the MotionSense wearable system will be used by patients undergoing TKA surgery leading up to and after their surgery. The patients will be using the system to monitor their recovery during daily activities, log daily pain scores and patient reported outcomes while also supporting their prescribed home exercise program. Each patient will thereby participate in outpatient physiotherapy in line with their current standard of care, while the physiotherapist will leverage the opportunities of the presented platform to give the patient personalized reminders for their patient-

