3.0 Research Plan

3.1 Study Design

The study is designed as a prospective, observational study including a maximum of 50 patients that are scheduled for total knee arthroplasty and will be participating in outpatient physiotherapy as part of their standard of care recovery pathway.

The study aims to replicate an actual use scenario of the Motionsense system, involving longitudinal follow-up of the patients starting 2-4 weeks prior to surgery up to 90 days after surgery. Patients will be recruited through the surgeon clinic, and subsequently use the MotionSense system at home and in collaboration with their physiotherapist who will assign adequate exercises to the patient. At the end of their 90-day recovery window, the patients' experience with the MotionSense system will be evaluated using a phone interview by the research nurse.

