3.2 Patient Journey

The patients will be using the Motionsense system for up to 120 consecutive days during this study. During the study, the patients will be interacting with the **principal investigator (PI)**, **physiotherapist (PT)** and **research nurse (RN)** at the following time intervals:

- **Initial Checkpoint:** patient consent and enrolment
 - Introduction to the study and patient consenting by Principal Investigator
 - System introduction (involving IFU – see Appendix A) and installation by Research Nurse
 - Initial, pre-operative exercise prescription (by Surgeon)
 - Evaluation of comorbidities (Charlson Comorbidity Index – Patient Reported)
 - Evaluation of expectations (HSS Expectations)
- **Pre-operative at home use:** prehab and questionnaires
 - Patient reported outcomes collected through app: KOOS and PROMIS-10 questionnaires
 - Daily pain scores
 - Pre-operative home exercise program completed
 - Pre-operative gait assessment (incl. use of walking aids)
 - Baseline activity data for activities of daily living (steps, weight bearing time, knee active time, range of motion)
- **Day of Discharge:** 2 to 3 days after surgery
 - Home exercise program updated by Surgeon
 - LACE questionnaire (Research Nurse)
- **Post-operative at home use:** home exercise and questionnaires
 - Patient reported outcomes collected through app: KOOS and PROMIS-10 questionnaires (at 2weeks / 6weeks / 90 days post-operative)
 - Daily pain scores
 - Post-operative gait assessment (2 times per week)
 - Post-operative home exercise program completed
 - Monitoring of daily activities

- **Outpatient Physiotherapist Visit:** starting 7-14 days after surgery
 - Home exercise program updated by Physiotherapist
 - Review of ADL activity by Physiotherapist
 - Changes in home exercise program documented and motivated in PT journal
- **Remote Monitoring:** throughout
 - Home exercise compliance and ADL activity level reviewed by Research Nurse / Surgeon
 - Logging of surgical complications (ER-visits / re-admissions / ...)
- **Final Checkpoint:** phone interview by Research Nurse
 - System compliance – evaluate moment of drop-off
 - Usability questionnaire including Net Promoter Score

Beyond these checkpoints with the health care professionals involved in the study, the patient will use the system on a daily basis and will be asked to fill out a daily pain score through the mobile application. The patient's daily flow while at home will look as follows:

- Wake-up

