5.0 Study Outline

Timescale	Tasks & Environment		
	Surgeon Clinic	PT Clinic	Home
2-3 weeks prior to surgery	
 ○ Patient Consent ○ Onboarding with MotionSense (incl. timing) ○ Fill out patient journal ○ Assign pre-operative exercises 	N/A	N/A
Prior to surgery	N/A	N/A	
 ○ Home exercises ○ Gait assessment (2x / week) ○ Pain scores ○ PROMs (KOOS & PROMIS10)
Day of Surgery	N/A	N/A	N/A
Discharge	
 ○ Re-install MotionSense sensors ○ Complete LACE questionnaire ○ Assign early-post-operative exercises 	N/A	N/A
After discharge	
 ○ Log complications / interactions with the clinic (e.g. additional patches) 	Log assigned exercises and reason for assignment Log active / passive range of motion	
 ○ Perform home exercises using sensor ○ Wear sensors during daily activities ○ Complete gait assessments (2x / week) ○ Report pain scores ○ Complete PROMs ○ Upload wound pictures as deemed necessary
90d after surgery	
 ○ Phone interview with patient 	N/A	N/A

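### The skin criterion does not name known adhesive reactions, so read literally it admits such patients to about 14 to 17 weeks of intended patch wear

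*Protocol*

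**What the plan says.** Protocol section 3.7 introduces its list with "More specifically, the following selection criteria will be used". Five criteria follow: unilateral knee replacement planned within four weeks, age 50 to 80, BMI of at most 35, smartphone ownership, and one on skin: "Patient does not have severe skin conditions that would potentially result in irritation or harming the skin when applying the weekly patches". The other four do not bear on how the skin tolerates a patch.

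On wear, section 1.0 says that "the weekly patches are first applied to the patients' skin and intended to stay on for at least a week". The patches carry sensor nodes above and below the knee. Section 3.2 says that "the patient will use the system on a daily basis", and on duration: "The patients will be using the Motionsense system for up to 120 consecutive days during this study". Section 3.1 gives the window as "starting 2-4 weeks prior to surgery up to 90 days after surgery", while the table in section 5.0 places consent and onboarding at "2-3 weeks prior to surgery". On supply, section 3.6 states: "Initially the patient will be provided with 9 x 2 weekly patches, upon request more weekly patches can be obtained through the surgeon clinic".

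**The concern.** The purpose of the skin criterion and the test it applies do not coincide. The purpose is to avoid irritation or harm from the patches. The test is whether the patient has a severe skin condition, and the words about irritation only qualify which severe conditions count. A known reaction to adhesives, tapes or dressings is a history. The skin may look entirely normal on the day of screening.

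The first thing at stake is patient safety in a case that one question could foresee. The second is consistent screening: staff who read the clause narrowly would enrol a patient whom staff who read it broadly would turn away. The third concerns interpretation. OBJ1.1 uses hours and days of use as measures of compliance. If a patient stops because of a reaction that could have been known beforehand, that stop is hard to separate from unwillingness or inconvenience.

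**Working it through.** **1. Apply the criterion to a test case.** Take a patient with healthy skin who has previously reacted to a skin adhesive, and who meets the age, BMI, surgery and smartphone criteria.
- Is there a skin condition? No.
- Is it severe? The question does not arise.
- Result on the literal wording: eligible.
- Result if the irritation clause is read as the real test: excluded at the investigator's discretion.

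The two readings give opposite answers for the same patient.

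**2. Look for another place that would catch this patient.**
- Protocol 3.2, initial checkpoint: consent, system introduction with the instructions for use, exercise prescription, patient-reported Charlson comorbidities, expectations. No question on adhesives is listed.
- Protocol 3.8, patient journal: described as covering comorbidities, socio-economic status and expectations. The form itself was not supplied.
- Protocol 5.0, study outline: no skin or adhesive check in any cell.
- SAP 1.2.1: adverse events are safety parameters. This records a reaction after it happens and does not screen for it.
- Instructions for use (Appendix A) and consent form (Appendix B): not available, so their content is unknown.

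**3. Intended exposure.** Inputs: pre-operative period of 14 to 28 days and 90 days after surgery (3.1); stated maximum of 120 days (3.2); discharge 2 to 3 days after surgery (3.2), when the sensors are re-installed (5.0).

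The plan's own figure first: 28 + 90 = 118 days, within 2 days of the stated maximum of 120. It reproduces.

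Window before allowing for the hospital stay:
- shortest: 14 + 90 = 104 days; 104 / 7 = 14.9 weeks
- longest: 28 + 90 = 118 days; 118 / 7 = 16.9 weeks

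Net of the hospital stay, assuming that no patches are worn from surgery to discharge:
- shortest: 14 + 90 − 3 = 101 days; 101 / 7 = 14.4 weeks
- longest: 28 + 90 − 2 = 116 days; 116 / 7 = 16.6 weeks

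With the start of 2 to 3 weeks in section 5.0, the upper end before the hospital stay is 21 + 90 = 111 days, or 15.9 weeks. Sections 3.1 and 5.0 should be reconciled, but about 14 to 17 weeks covers both.

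**4. Check that this is intended wear, not guaranteed wear.** The initial 9 pairs of weekly patches, changed every 7 days, last 9 × 7 = 63 days. That is 63 / 104 = 61% of the shortest window and 63 / 118 = 53% of the longest. The rest needs refills, or each pair must stay on for about 104 / 9 = 11.6 to 118 / 9 = 13.1 days. Since the patches are meant to stay on for at least a week, a count of one change per week is an upper limit.

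**5. What cannot be computed.** The documents give no rate of adhesive reaction, no expected level of compliance and no expected time to stopping. No count of affected patients and no effect on OBJ1.1 follows from them.

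**The case against.** The strongest case on the other side has four parts.

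*The clause already covers these patients.* It ties the condition to its effect on the skin, and a sensible investigator could treat a known adhesive reaction as falling within it. This stands as far as it goes. A reader might infer that the protocol knowingly admits such patients, and it does not say so. But a criterion that gives opposite answers under two fair readings is still worth one added phrase.

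*A screen may exist elsewhere.* Onboarding uses the instructions for use, and device warnings could sit there or in the consent form. A reader might infer that no safeguard exists anywhere. That cannot be concluded, because those documents were not supplied. What can be said is that such a warning would not be among the selection criteria listed in section 3.7.

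*The word severe may be deliberate.* A reader might also object that mild or moderate skin conditions pass. The documents do not support calling that a defect. Section 3.1 aims to replicate actual use and section 3.7 wants typical intended users, some of whom will have minor skin conditions. Admitting them is a defensible choice.

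*Stopping because of the patches is itself a usability result.* The final interview in section 3.2 asks when use dropped off, and the SAP collects adverse events. This is right. A reader might infer that early stoppers would lower measured compliance by some definite amount, but that does not follow. SAP section 1.4.4 restricts analysis to subjects who are not censored and to a per protocol population, and the supplied text defines neither. Early stoppers may be counted or may drop out of the analysis, so even the direction of any effect is open.

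**Conclusion.** The point holds as a gap in the listed criteria. Section 3.7 means to protect patients whose skin the patches could harm, but its literal test misses those with healthy skin and a known adhesive reaction. Their intended exposure is 101 to 116 days, or 14.4 to 16.6 weeks, on the leg being operated on. This rests on the window in section 3.1, discharge at 2 to 3 days, and no patch wear between surgery and discharge. It is the planned duration; a patient who reacts may well stop sooner.

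The finding does not depend on how common such reactions are and makes no claim about the size of any bias. It invalidates no objective of this descriptive study of at most 50 patients. The change is still worth making, because it serves the criterion's own purpose and improves safety at almost no cost.

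**What to change.** Keep the existing wording on severe skin conditions in section 3.7 and add: *and no known allergy or previous reaction to skin adhesives, tapes or dressings that in the investigator's judgement could lead to irritation or harm from the patches.*

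Ask about this once at the initial checkpoint in section 3.2, before the first patch is applied, and report the number of patients screened out for this reason. That number shows readers how many candidates could not be offered the system.

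The cost is one added phrase, one screening question and one line in the report. The downside is that a few patients are excluded, and the usability conclusion then applies only to patients without known adhesive sensitivity; the report should say so.

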3.8 Data Collection

In general, the data collection in this study is focused on assessing the primary and secondary goals of the study as listed in section 2.0. This leads to various sources of data collection:

- **Patient journal:** pre-operatively, the patient will fill out a number of questionnaires on paper form to frame potential comorbidities / socio-economic status / expectations.
- **Physiotherapist journal:** the physiotherapist will fill out a document following each physiotherapy visit to document the prescribed exercises along with the motivation for assigning these exercises and setting the targets for these exercises.
- **Wearable & App data capture:** during the patients' daily use of the wearable and interaction with the mobile application, the sensor will capture activities of the patients' daily life as well as their exercise completion by storing a series of variables on the patient's phone and sharing this data to a HIPAA compliant database. More specifically, this data capture involves:
 - **ADL:** the patients' activities of daily living is captured by the sensors, involving an hourly histogram of the patients knee flexion angle, an hourly total of a patients' active minutes, an hourly total of a patients' weight bearing time, an hourly total of a patients' time wearing the sensor.
 - **Gait:** at predefined time intervals (2 x per week), the patient will be prompted to walk for 1 minute while the sensors log the raw signals and share this data with the OrthoLogIQ database. This data can be further evaluated from cloud, looking at cadence, range of motion during gait, ...
 - **Exercises:** the performed exercises and completion of the daily exercises will be recorded by the mobile application.
 - **Pain scores:** the patient will be asked to report their daily pain scores through the mobile application.
 - **Patient Reported Outcomes:** patients will be asked to complete a KOOS and PROMIS-10 questionnaire through the mobile application at distinct time intervals throughout their recovery pathway.
- **Patient interviews**
 - At the end of the study, the patient will join a phone interview while responding to a series of usability questions specific to their use of MotionSense during the recovery after surgery. In addition, the patient will be asked about any complications and/or re-admissions that they experienced during their 90d recovery window after surgery.

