## 1.3 Missing Data

No missing data will be imputed.

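### KOOS and PROMIS-10 have the app as their only stated route, so patients who stop using the app have no 90-day score, although the research nurse phones patients at that time

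*Protocol*

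**What the plan says.** **Route of the questionnaires.** Protocol 3.8 states that "patients will be asked to complete a KOOS and PROMIS-10 questionnaire through the mobile application". Protocol 3.2 also gives the app as the route, before surgery and at the three post-operative times, the last at 90 days. The table in Protocol 5.0 places the post-discharge questionnaires under the home setting.

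**Paper forms.** Protocol 3.8 mentions paper once: "pre-operatively, the patient will fill out a number of questionnaires on paper form". These cover comorbidities, socio-economic status and expectations, not KOOS or PROMIS-10.

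**The day-90 call.** Protocol 3.1 says: "At the end of their 90-day recovery window, the patients' experience with the MotionSense system will be evaluated using a phone interview", made by the research nurse. Protocol 3.2 lists its content as when the patient stopped using the system, and usability with a Net Promoter Score. Protocol 3.8 adds that "the patient will be asked about any complications and/or re-admissions that they experienced during their 90d recovery window after surgery". KOOS and PROMIS-10 are not listed.

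**Analysis.** SAP 1.3 states: "No missing data will be imputed". SAP 1.4.4 bases the objective analyses on a per protocol population that it does not define further. SAP 1.4.1 plans descriptive summaries and Spearman correlations. No comparison of responders with non-responders and no sensitivity analysis is planned.

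**The concern.** The app is part of the system whose uptake is being studied, and it is also the instrument that collects the patient-reported outcomes. Compliance with the system is a primary objective (OBJ1.1). Stopping the app therefore does two things at once: it is a compliance result, and it removes the later KOOS and PROMIS-10. The protocol expects some patients to stop, since the final call asks when use ended.

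Two results are exposed. The first is any 90-day summary of KOOS or PROMIS-10 under the general descriptive plan in SAP 1.4.1. The second is OBJ2.1 where a pre-operative or early sensor metric is correlated with a 90-day score. Both would be computed on persistent app users, although Protocol 3.7 deliberately seeks patients with differing motivation. A score not collected at day 90 cannot be obtained later, and the SAP offers no analytic remedy.

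**Working it through.** The plan has no figure to reproduce: SAP 1.4.2 reports no sample size calculation, and neither document gives a drop-off rate or an SD. The documents settle the structure; the size can only be shown over assumed ranges.

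**Structure.** Three facts set side by side give the result:

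1. KOOS and PROMIS-10 come through the app (Protocol 3.2 and 3.8).
2. The only contact that does not depend on the app and is scheduled at day 90 is the call, whose listed content omits them (Protocol 3.2 and 3.8).
3. Nothing missing is filled in (SAP 1.3).

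Followed as written, a patient off the app at day 90 has no 90-day score.

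**Inputs.** N = 50 (Protocol 3.7; 3.1 calls it a maximum). Assumed: share who stop the app, q = 20–40%; difference between persisters and stoppers, d = 0.25–0.8 SD; share of stoppers who complete the forms at the call, f = 50% or 80%.

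**Error in the completer mean.** The full mean is (1 − q) × persister mean + q × stopper mean, so the completer mean is off by q × d.

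| q | n with a 90-day score | d = 0.25 | d = 0.5 | d = 0.8 |
|---|---|---|---|---|
| 20% | 40 | 0.05 | 0.10 | 0.16 |
| 30% | 35 | 0.075 | 0.15 | 0.24 |
| 40% | 30 | 0.10 | 0.20 | 0.32 |

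The range is 0.05–0.32 SD. For scale, the 95% half-width of a mean is 1.96/√n SD: 0.28 SD at n = 50 and 0.33 SD at n = 35.

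**Stronger selection.** A simulation of 2,000,000 bivariate normal pairs (correlation 0.3) let the odds of stopping rise 2- to 3-fold per SD of worse outcome. The completer mean then shifts by 0.19–0.27 SD at 30% stopping, and by 0.13–0.36 SD over 20–40%. At 30% these odds ratios imply a gap between persisters and stoppers of 0.19/0.30 = 0.63 to 0.27/0.30 = 0.90 SD, so they sit at the strong end of the assumed range or beyond it.

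**Correlation.** In that simulation Spearman rho is 0.287 in everyone and 0.265–0.276 in those retained at 30% stopping. The bias is about 0.01–0.02 there, and within about 0.01–0.03 over 20–40%. For precision, take Fisher z with SE = √((1 + rho²/2)/(n − 3)) and rho = 0.3:

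- n = 50: SE = √(1.045/47) = 0.149, 95% CI 0.02 to 0.54
- n = 35: SE = √(1.045/32) = 0.181, 95% CI −0.04 to 0.58

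**Effect of using the call.** With a share f of stoppers recovered, the number of scores is N(1 − q + fq) and the remaining error is d × [q − fq/(1 − q + fq)]. At q = 30% and d = 0.5:

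- f = 80%: n = 50 × 0.94 = 47; error = 0.5 × (0.30 − 0.24/0.94) = 0.02 SD
- f = 50%: n = 50 × 0.85 = 42.5; error = 0.5 × (0.30 − 0.15/0.85) = 0.06 SD

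Both compare with 0.15 SD under app-only collection. Over q = 20–40% and d = 0.25–0.8, recovering 80% leaves 0.01–0.04 SD.

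**The case against.** The case against acting is substantial.

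- **App-only collection is partly deliberate.** The study is meant to mirror real use, and questionnaire completion is a primary compliance measure, so non-completion is itself a finding. This stands. It is a reason to keep the compliance count in-app, not a reason to forgo the score.
- **The mean shift concerns no named objective.** OBJ2.3 lists pain, steps, active and weight-bearing time, range of motion and gait, not KOOS or PROMIS-10. The objective that uses the scores is OBJ2.1, which is secondary, and there the simulated bias is small. This stands and lowers the severity.
- **Precision gains are modest.** If half the stoppers are reached (n about 42), the interval for rho = 0.3 is −0.01 to 0.56 instead of −0.04 to 0.58. This stands.
- **Recovery is partial.** Stoppers may also lack 90-day sensor data, so same-time pairs stay missing. The recoverable pairs join earlier sensor metrics to the 90-day score, and OBJ2.1 does not specify which pairs it intends. This stands.
- **Protocol 3.4 makes the research nurse responsible for seeing that forms are completed.** The scope of that duty is unclear and it names no alternative route, so it does not answer the point.
- **The interview form and appendices were not in the text reviewed.** That the app is the only route is inferred from the absence of any other. If the form already includes the questionnaires, the protocol should say so.

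A reader might infer that patients who stop have no 90-day outcome at all. The documents do not support that: complications, re-admissions and usability are still collected by phone, and physiotherapists log range of motion after discharge (Protocol 5.0). Nor does taking off the sensors lose the scores, since such a patient can still answer in the app.

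**Conclusion.** The point holds for the 90-day KOOS and PROMIS-10 only. As written, these scores come from patients still using the app, and nothing in the SAP offsets that.

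The size rests on assumptions, because the documents give neither a drop-off rate nor a difference between stoppers and persisters. With 20–40% stopping and a difference of 0.25–0.8 SD, the completer mean is off by 0.05–0.32 SD. At 30% stopping, 15 of 50 pairs are lost. The effect on rho is mainly lost precision.

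A reader might infer that the 90-day results would look too favourable. That is plausible but not established: patients who are doing badly may stop, and so may patients who have recovered and no longer see a need for the app. The documents give no direction.

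Severity is minor to moderate. The objective is secondary and descriptive, with no hypothesis test or sample size target, but the loss is permanent and cheap to reduce.

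**What to change.** 1. **Protocol 3.2 and 3.8.** At the existing day-90 call, offer any patient with no in-app 90-day KOOS and PROMIS-10 the choice of completing them by phone or on paper. Record the mode.
2. **OBJ1.1.** Count only in-app completions in the questionnaire-completion measure, so that the compliance result is unchanged.
3. **SAP 1.4.4.** State that patients who stop using the app stay in the population for OBJ2.1 and for the KOOS and PROMIS-10 summaries. Without this, the undefined per protocol population could exclude the recovered forms.
4. **SAP 1.4.1.** Report the number of scores at each time point by mode. Give results for all completions and for in-app completions only. Note that the difference mixes mode with selection, because phone or paper answers come only from patients who did not respond in the app. Compare baseline KOOS and PROMIS-10 by mode and response status.

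**Cost.** A longer call for a subset of patients, with no new staff. The documents give no questionnaire length, so the added time is not quantified. A mode effect is possible, since the caller is employed by the surgeon's office (Protocol 3.7), and item 4 can display it but not isolate it. Same-time 90-day sensor pairs for stoppers remain missing.
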